The sample size estimate to determine primary endpoint is based on the primary objective of demonstrating non-inferiority of the test group to the control group at 3

months. Established methods were followed in determining the non-inferiority criteria and the related sample size estimate

- Test basis: Farrington-Manning binomial test for non-inferiority
- Estimated responder rate of 70% in the test group and 50% in the control group
- Significance level, alpha, of 0.05 one-sided
- Statistical power = approximately 90% or greater
- Non-inferiority margin of 10%
- Randomization: 1:1

Based on these assumptions, a minimum of 50 randomized and trialed subjects per treatment group (100 total) are required.

B.5.5.2 Overall Sample Size and Enrollment

Based on the primary endpoint requirement, a minimum of 50 subjects per treatment group are required (100 total). To account for a combined estimated attrition of 25% for subjects that do not complete the Trial Phase, and subjects that exit study before the 3-month primary endpoint visit, approximately 135 subjects would need to be randomized and trialed.

To account for 46% attrition prior to randomization (including subject ineligibility after signing the informed consent and subject dropout), it is estimated that a total of up to 250 subjects would need to be enrolled in the study.

B.5.6. Study Duration

This study is expected to last approximately 32 months. Enrollment of subjects is expected to last 18 months. Subjects who are expected to complete the study will commit to it for approximately 14 months. This consists of Baseline assessments, up to 10 days of trial stimulation, and 12 months of treatment following implantation and activation of the device.

B.5.7. Interim Administrative Analyses

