At the end of the Trial Phase, subjects will be assessed for pain intensity under optimal therapy parameters. Anterior-posterior (AP) and lateral X-ray imaging may be done at the end of the Trial Phase. The subject will be assessed for adverse events and medication usage.

Those who have a "successful Trial Phase" (defined as a 40% or greater pain reduction from Baseline in their back pain) will proceed to permanent implantation of a SCS system to evaluate the assigned therapy, and permanent implantation of the Intellis™ SCS system will be scheduled. A threshold of 40% for the Trial Phase was predetermined as the minimum pain reduction that warrants consideration of a permanent implant and an

opportunity to achieve a 50% pain reduction as defined in the Individual Subject Success criterion (see Section B.7.3.).)

Data from subjects who did not achieve 40% or greater pain reduction in back and do not receive permanent implantation will be carried forward toward the primary and secondary endpoints. These subjects will exit the study after being followed up for two weeks after explant of the leads to assess adverse events.

B.6.8. Permanent Device Implant (0-60 days from end of successful Trial Phase)

As described in section B.6.7, subjects who underwent a successful trial of the assigned SCS therapy and who agreed to continue into the next stage of the study will proceed to permanent implantation stage.

Permanent percutaneous leads will be placed in the epidural space at a vertebral level based on the subject's pain condition and pain pattern as described in the Intellis™ Physician Implant Manual. The INS will be implanted by a trained physician according to standard practice and following the Physician Implant Manual for the device. Anterior-posterior (AP) and lateral X-ray imaging will be obtained. Standard practice of a study site for prophylactic pre-surgery antibiotics and post-surgery pain medications will be followed). Subjects will be assessed for adverse events and medication usage.

B.6.9. Device Activation (0-14 days following Permanent Implant)

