- Acetaminophen, NSAIDs or other pain medications (new prescriptions or greater than Baseline doses) may only be taken for an acute condition and for a limited duration. For each type of pain medication, dosing should not exceed the maximum daily dosage recommended by the manufacturer and usage should not continue beyond 5 days. Should acute pain medication usage coincide with a follow-up visit, the visit will be postponed until two weeks after acute pain medication usage has been stopped.
- Following trial and permanent implants, the clinical site's standard practice for prophylactic pre-surgery antibiotics and post-surgery pain medications will be followed. Investigators will instruct subjects not to change usage of any other concomitant pain medications.

B.6.18. Device Explant

At any time during the study, a subject may elect to withdraw from the study and have the SCS device system explanted. Additionally, an Investigator may elect to explant a device due to an adverse event.

The Investigator must follow the appropriate guidelines set forth by the Medtronic for returning the explanted device and/or lead(s) as well as the accessories (charger, patient remote control).

B.6.19. Early Subject Withdrawal

Although efforts will be made by Investigators and study staff to encourage subjects to remain enrolled in the study, subjects may withdraw early from the study for a number of reasons, including but not limited to:

- Failure of SCS Trial Phase
- Subject request
- Investigator request
- Subject lost to follow-up
- Subject's death
- Adverse events (e.g., intolerable adverse event occurrence that forces subject to stop participation in the study)

If a subject is considering withdrawing from the study due to unsatisfactory effectiveness of the assigned treatment, the Investigator will make attempts to improve therapy during a study visit. When a subject is withdrawn early from the study, a Study Termination eCRF will be completed describing the reason for discontinuation. Study staff will contact subjects to remind them about their scheduled visits and make sufficient efforts to locate a subject that is not responding to a contact call. In situations where study withdrawal is due to an adverse event, subjects will be followed until resolution of the adverse event or determination that the adverse event is not likely to change.

B.6.20. Study Completion

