B.7. Study Endpoints

B.7.1. Definition of Analysis Populations

- Modified Intent to Treat (mITT): All successfully randomized subjects who complete the Trial Phase.
- Intent-to-Treat (ITT): All successfully randomized subjects who met all the enrollment criteria.
- Per-Protocol (PP): All subjects who received a permanent device implant and contributed their data to the 3-month endpoint without any major protocol deviations or adverse events (that would render their data unevaluable).

The primary analysis of the primary and secondary endpoints will be performed on the mITT population. Supportive analyses will be performed for the Intent-to-Treat and Per-Protocol population.

For analyses incorporating crossover data (i.e. data gathered in the post 6-month periods), analyses will be based on the mITT population with treatment group defined by the treatment status at the corresponding time point to capture the impact of crossover. Additional sensitivity analyses censoring data post-crossover will be performed to examine the impact of crossover.

B.7.2. Effectiveness Assessment Definitions

- Primary Effectiveness Assessment: For subjects who have a successful Trial Phase and receive a permanent implant, the Primary Efficacy Assessment occurs at the follow up visit 3 months after Device Activation. For subjects who do not have a successful Trial Phase (based on subject's pain score) or subjects who do not want a permanent device implant due to insufficient pain relief (based on subject's discontinuation reason), the Primary Efficacy Assessment occurs at the end of the Trial Phase.

B.7.3. Primary Endpoint

Pain rating on the 10 cm Visual Analog Scale is considered the primary outcome measure. VAS is the most widely used outcome measure in assessing pain due to its documented reliability and validity, ease in administration, and minimal training requirements for the administrator.

- ***Individual Responder:*** A decrease in back pain VAS by at least 50% at 3 months after Permanent Device Activation as compared with Baseline. All subjects must be using the assigned programming parameters. If a subject is switched to a programming parameter that is not considered to be DTM-SCS nor Conventional SCS programming the subject will be counted as a non-responder for the following follow-up visit if one of the two following conditions exist:

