 - If a subject is switched to a programming parameter that is not considered to be DTM-SCS nor Conventional SCS programming for a period over two weeks
 - If a subject is switched to a programming parameter that is not considered to be DTM-SCS nor Conventional SCS programming for any length of time within the 2 weeks prior to a follow-up visit.

Overall Study Success: The percentage of Individual Responders in the test group is shown to be statistically non-inferior to the percentage in the control group.

B.7.4. Secondary Endpoints

The following secondary endpoints will be evaluated:

- Comparison of the percentage of Individual Responders between the test and control groups in a statistical test of superiority over time (i.e. based on repeated measures analysis). In addition, data will be summarized at the individual time points at 3 months, 6 months, 9 months, and 12 months. This will be performed based on all observed data with treatment defined as a time dependent covariate, and additionally based on censoring data post-crossover.

- Comparison of change from Baseline in back pain score (VAS) between test and control in statistical tests of non-inferiority and superiority. This is calculated as: Change from Baseline in Back Pain VAS = Follow-up Visit Pain VAS – Baseline Pain VAS. A negative result reflects a decrease in the Pain VAS, while a positive result reflects an increase in Pain VAS. All subjects must be using the assigned programming parameters. If a subject is switched to a programming parameter that is not considered to be DTM-SCS nor Conventional SCS programming, that subject's Baseline Back Pain VAS will be used instead of Follow-up Visit VAS after the programming change has occurred for the following follow-up visit if one of the two following conditions exist:
 - If a subject is switched to a programming parameter that is not considered to be DTM-SCS nor Conventional SCS programming for a period over two weeks
 - If a subject is switched to a programming parameter that is not considered to be DTM-SCS nor Conventional SCS programming for any length of time within the 2 weeks prior to a follow-up visit.

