Missing data will be minimized by rigorous follow-up and investigator and site training. Additionally, for subjects who do not have a successful Trial Phase, results from the Trial Phase will be utilized for the primary endpoint as described in Section B.7.2. Effectiveness Assessment Definitions. Any other data will be imputed via Multiple Imputation. Additionally, sensitivity analyses for missing data will be performed. Unless otherwise specified, all other analyses will be based on the evaluable data with no imputation.

Details on imputation will be provided in a separate statistical analysis plan.

C. Risk Analysis

C.1. Description and Analysis of All Increased Risks to Subjects

Spinal Cord Stimulation (SCS) Risks:

DTM-SCS programming approach will be used with commercially available, FDA approved Intellis™ SCS system within approved indications for use. Anticipated potential adverse events resulting from the study are expected to be in line with adverse events already documented for SCS using a Standard programming approach.

There are known risks associated with the use of any SCS system. Known risks are associated with the implant procedure, the stimulation, the implanted device (not associated with stimulation) and external devices such as the charger and remote control. These are typical of commercial SCS systems. Subjects will be informed of these anticipated risks in the study consent process.

Risks of Surgery

Implanting a neurostimulation system has risks similar to spinal procedures, including spinal fluid leak (spinal fluid collection under the skin), headaches, swelling, bruising, bleeding, infection, or paralysis.

Subjects on anticoagulation therapy may be at higher risk for problems after surgery such as hematomas that could result in paralysis.

Spinal Cord Stimulation Risks

The implantation of a spinal cord stimulation system involves risks that are similar to other spinal procedures. In addition to those normally associated with surgery, implantation or use of a neurostimulation system includes, but is not limited to the following risks:

- Allergic or immune system response to the implanted materials
- Infection
- Lead or neurostimulator erosion through the skin or migration
- Leakage of cerebrospinal fluid
- Loss of pain relief may return patients to their underlying pain condition
- Persistent pain at the neurostimulator site

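### Back-pain responder rates at 6, 9 and 12 months drop implanted subjects who are explanted or withdraw for insufficient relief, which inflates each arm's descriptive durability figures

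*Combined protocol and SAP*

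**What the plan says.** B.7.4 lists the comparison of Individual Responders over time as a secondary endpoint, with summaries at 3, 6, 9 and 12 months. On the data to be used it says: "This will be performed based on all observed data with treatment defined as a time dependent covariate". A second version censors data after crossover. B.9.2.4 sets the general default: "Unless otherwise specified, all other analyses will be based on the evaluable data with no imputation". It also mentions Multiple Imputation and missing-data sensitivity analyses, and leaves the imputation details to a separate statistical analysis plan.

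Loss after implant is foreseen. B.6.18 allows that, at any time, "a subject may elect to withdraw from the study and have the SCS device system explanted". B.6.19 expects some subjects to consider leaving because the treatment does not work well enough, and has the reason for early withdrawal recorded on the Study Termination eCRF.

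For trial failures, B.6.7 says that their data "will be carried forward toward the primary and secondary endpoints". B.7.1 makes mITT (randomized subjects who complete the Trial Phase) the main set for primary and secondary endpoints. For data after month 6 it uses "treatment group defined by the treatment status at the corresponding time point".

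B.9.2.2 gives the repeated-measures responder comparison no hypothesis and no significance level. B.8.2 rests study success on the primary non-inferiority test alone.

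**The concern.** A subject whose device is removed for lack of relief after month 3 has no later VAS score. Under an observed-data rule that subject is not a failure at month 12 but is simply absent. The repeated-measures logistic GEE in B.9.2 does not repair this: without weighting or imputation it relies on loss being unrelated to response, and exits for insufficient relief are related to it by definition.

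The plan is stricter elsewhere. B.7.3 and B.7.4 score a subject moved to programming of neither study type as a non-responder at the next visit, subject to timing conditions. A subject who gives up the device for lack of relief has no such rule.

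At stake are the 6- to 12-month responder rates, which a reader will take as evidence that relief lasts. As planned they describe subjects who are still being treated and assessed. Because exits accumulate, the inflation grows with each visit and can hide a decline.

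**Working it through.** **The plan's own figures.** B.5.5.1 assumes that 70% of test and 50% of control subjects respond. It tests at a one-sided 5% level with a 10-point margin and 1:1 allocation, and aims for power of about 90% or more. Farrington-Manning power is Φ[(√n × (pT - pC + m) - 1.645 × s0)/s1].

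- The restricted null rates are 0.544 and 0.644, so s0 = √(0.544×0.456 + 0.644×0.356) = 0.691.
- s1 = √(0.7×0.3 + 0.5×0.5) = 0.678.
- At n = 50 per arm: (7.071×0.30 - 1.645×0.691)/0.678 = 1.45, which is 92.7% power. The stated 50 per arm is adequate.
- 100/0.75 = 133.3, so 134 against the stated 135.

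These concern month 3 and are not in dispute. The 25% attrition in B.5.5.2 stops at the 3-month visit, and the plan gives no figure for later loss.

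**Effect of the observed-data rule.** Let R be an arm's month-12 rate in the mITT set with exits for insufficient relief counted as non-responders, and w the share of mITT subjects lost that way. Trial failures are kept in, as B.6.7 provides, and there is no other missing data. The responders are unchanged and the denominator shrinks:

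reported rate = R/(1 - w)

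The values of R and w below are assumptions.

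| R | w = 5% | w = 10% | w = 15% |
|---|---|---|---|
| 60% | 63.2% | 66.7% | 70.6% |
| 40% | 42.1% | 44.4% | 47.1% |

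In head counts, with 50 mITT subjects in an arm, R = 60% is 30 responders. If 5 subjects leave for insufficient relief, the report shows 30/45 = 66.7%.

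**Effect on durability.** Suppose the rate is 70% at month 3, with no such exits yet, and truly 60% at month 12. With w = 15% by month 12 the report shows 70.6%, and the fall disappears.

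**Effect on the between-arm difference.** Take R = 70% and 50%, a difference of 20 points.

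- w = 5% test, 15% control: 0.70/0.95 = 73.7%; 0.50/0.85 = 58.8%; difference 14.9 points.
- w = 10% in both: 0.70/0.90 = 77.8%; 0.50/0.90 = 55.6%; difference 22.2 points.

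The difference can shrink or grow, so no direction is established.

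**The case against.** **The missing-data rule is not fully settled.** In B.7.4 the reference to all observed data is set against censoring at crossover, so it partly describes crossover handling. The Multiple Imputation sentence in B.9.2.4 could be read broadly, sensitivity analyses are promised, and details are deferred. This stands in part. But the imputation sentence follows the primary-endpoint rule, and the no-imputation default comes right after it. The sensitivity analyses have no stated content, and the crossover-censored version also removes later data from subjects who crossed over for insufficient relief.

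**Loss need not reflect failure.** B.6.19 also lists subject and investigator request, loss to follow-up, death and adverse events, and the month-6 crossover gives dissatisfied subjects a reason to stay. This stands: the point covers only exits for insufficient relief, and the effect is zero if there are none.

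**Trial failures.** A reader might infer that trial failures also leave the denominator, since B.9.2.4 names their Trial Phase result for the primary endpoint only and they have no current treatment. With 10% and 20% trial failures added to the 5%/15% exits, the rates would become 0.70/0.85 = 82.4% and 0.50/0.65 = 76.9%, a difference of 5.4 points. The documents do not support building on this. B.6.7 carries these subjects into the secondary endpoints, B.7.1 includes them in mITT, and the B.9.2.4 default yields to anything otherwise specified. What remains is a need to align the wording.

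**False rise.** A reader might also infer that dropping trial failures creates false durability, for example 70% at month 3 turning into a reported 0.60/0.80 = 75.0% at month 12 (10% trial failures, 10% exits). That mixes denominators. Applied at every visit, the same exclusion gives 0.70/0.90 = 77.8% at month 3, so the series still falls.

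**Consequence.** B.7.4 speaks of a superiority test, but B.9.2.2 attaches no significance level to the repeated-measures comparison. This stands and limits the point to descriptive reporting.

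**Conclusion.** The point holds for implanted subjects who are explanted or withdraw for insufficient relief. Followed as written, the plan inflates each arm's responder rate at months 6, 9 and 12 by a factor of 1/(1 - w): 1.05 at w = 5%, 1.11 at 10% and 1.18 at 15%. The upward direction within each arm follows from arithmetic once such exits occur. The size rests on assumed exit rates and on these subjects being non-responders.

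A reader might infer that the trial's main conclusion is at risk, or that the test arm is favoured. Neither is supported. Success depends on the 3-month test, this endpoint has no significance level, and the comparative effect depends on which arm loses more subjects. The long-term rates should be corrected because they are the study's durability evidence.

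**What to change.** In B.7.4 and B.9.2.4, for the 6-, 9- and 12-month back-pain responder rates:

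1. Keep every mITT subject in the denominator at each visit.
2. Count subjects explanted or withdrawn for insufficient relief as non-responders at all later visits, using the reason on the Study Termination eCRF.
3. State that trial failures are carried forward as non-responders at every visit, and align both sections with B.6.7.
4. Assign subjects without a current treatment to the last treatment received, which is the randomized arm for trial failures, or report the rates by randomized arm. This also settles subjects who cross over and are then explanted.
5. Handle other missing visits by Multiple Imputation, stating that it extends to these rates.
6. Count adverse-event explants as non-responders in a sensitivity analysis only. Whether they are failures is a choice of estimand, since some may have had good relief.
7. Keep the observed-data rates as supportive.

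No new data are needed. The cost is revised wording, one added table and long-term rates that look less favourable.

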Potential study subjects will be identified from a pool of candidates for SCS therapy that are either affiliated with or referred to the clinical sites. Notice of availability of the study may be used for recruitment purposes, upon approval of the patient recruitment materials by the study IRB(s). An informed consent form (ICF) will be given to the potential subject for private evaluation. The Investigator or Study Clinical Staff will be available to respond to any questions the potential subject may have during evaluation of the ICF. Potential study subjects willing to participate in the study will visit the study site for providing written consent and for evaluation of eligibility based on inclusion and exclusion criteria. Subjects may also be consented via a combination of mail and telephone calls. The RC will document the telephone calls and follow-up by signing the consent once the subject returns the signed consent. The RC will then provide a photo copy to the subject. Once a consented subject is deemed qualified to participate in the study, baseline assessments and randomization will occur followed by scheduling of the trial stimulation phase with the assigned treatment group. Subjects who complete a successful SCS trial phase will be scheduled to receive a permanent implant of leads and the implanted neurostimulator (INS) and will undergo 12 months of stimulation delivery with assessments at 1, 3, 6, 9, and 12 months after the activation of the therapy.

All subjects who remain implanted at or after the 6 month visit, but are not getting sufficient pain relief and would like to try the other treatment arm's parameters will have the option to cross over to the other treatment group (this is an optional two-way crossover). X-ray may be required to determine lead locations. Crossover must be completed within 30 days of the 6 month visit.

Baseline assessments will include measures for pain intensity, use of medication, extent of disability, and quality of life.

Following completion of the baseline assessment, study subjects will be randomized in a 1:1 ratio to either the DTM-SCS programming group or the Conventional SCS programming group.

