Subjects will visit the study site where they will be assessed for pain, extent of disability, quality of life, Patient Global Impression of Change, and subject satisfaction. Paresthesia generated by the stimulator will be assessed. Programming adjustments may be made, as needed. Anterior-posterior (AP) and lateral X-ray imaging may be done if significant lead migration is suspected. Subjects will also be assessed for possible adverse events and medication usage.

After the 6 month assessment is completed, subjects in both arms will have an option to change to the other arm if the subject is not receiving sufficient pain relief and desires to try the other arm's parameters. The subject can crossover immediately after completing the 6 month assessment or within 30 days after completing the 6 month assessment. At the time of crossover, imaging may be required to confirm lead location before programming. If the subject has gross lead migration and is not a candidate for a lead revision, the subject may have to be withdrawn due to the inability to program effectively. If withdrawn, the subject would be continued to be followed by their pain physician as a non-study, commercial patient.

B.6.15. 9 Months After Device Activation (\pm 31 days)

Subjects will visit the study site where they will be assessed for pain, extent of disability, quality of life, Patient Global Impression of Change, and subject satisfaction. Paresthesia generated by the stimulator will be assessed. Programming adjustments may be made, as needed. Subjects will also be assessed for possible adverse events and medication usage.

B.6.16. 12 Months After Device Activation (\pm 45 days)

The follow-up visit 12 Months after Device activation is the final scheduled study visit. Subjects will visit the study site where they will be assessed for pain, extent of disability, quality of life, Patient Global Impression of Change, and subject satisfaction. Paresthesia generated by the stimulator will be assessed. Programming adjustments may be made, as

needed. Subjects will also be assessed for possible adverse events and medication usage.

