Analysis of both secondary endpoints will be based on a repeated measures approach that accounts for within subject correlation. Treatment group status for the repeated measures models will be based on treatment status at the current time point (i.e. it will be based on treatment status incorporating potential crossover, not necessarily the original randomized assignment).

B.7.5. Additional Data Collection

These following data will be collected:

- Frequency of treatment emergent adverse events
- Comparison of opioid medication usage from baseline at 3, 6, 9 and 12 months after device activation between the two arms
- Comparison of mean change from Baseline in Leg Pain VAS, evaluated at 3, 6, 9 and 12 months after device activation for subjects with baseline leg pain VAS score ≥ 5 between test and control
- Comparison of Leg Pain Treatment Success, measured as at least a 50% reduction in Leg Pain VAS, evaluated at 3, 6, 9, and 12 months after device activation for subjects with baseline leg pain VAS score ≥ 5 between test and control
- Comparison of patient satisfaction between two arms
- Patient Global Impression of Change, evaluated at 3, 6, 9 and 12 months after device activation
- Comparison of Patient Global Impression of Change between two arms

- Comparison of ODI change from baseline at 3, 6, 9 and 12 months after device activation between the two arms
- Comparison of quality of life (QoL) change (from EuroQol EQ-5D-5L) from baseline at 3, 6, 9 and 12 months after device activation between the two arms
- Quality of paresthesia at 3, 6, 9 and 12 months, comparison between test and control
- Percentage of subjects that crossover
- Comparison of mean change from last visit prior to crossover to 12 months visit. This analysis censors data post-crossover.
- Activity level based on Intellis™ adaptive data log (when available)
- Analysis of additional evaluable data items will be based on treatment status at the current time point (i.e. it will be based on treatment status incorporating potential crossover, not necessarily the original randomized assignment).

B.8. Evaluation Criteria

B.8.1. Effectiveness

Results of the tests and standard questionnaires will be recorded in Case Report Forms at Baseline and during follow-up visits. Changes from Baseline will be calculated and compared between the two groups.

Effectiveness will be measured for each subject using the following tests:

- Pain

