Activity	Pre-Trial Phase			Trial Phase		Permanent Implant (up to 60 days after end of trial)	Permanent Implant Phase Follow-up					
	Enrollment	Baseline	Randomization	Start Trial Phase	End Trial Phase (up to 10 days after start of trial)		Device Activation (0-14 days after implant)	1-month visit (±15 days after activation)	3 months visit (±21 days after activation)	6 months visit (±31 days after activation)	9 months visit (±31 days after activation)	12 months visit (±45 days after activation)
Informed Consent	X											
Pain Intensity Evaluation (VAS)	X				X			X	X	X	X	X
Medication Use	X	X		X	X	X	X	X	X	X	X	X
Medical/Surgical History	X	X										
Eligibility Criteria Evaluation	X											
Disability Assessment (ODI)	X							X	X	X	X	X
Quality of Life Assessment (EQ-5D-5L)		X						X	X	X	X	X
Randomization			X									
AP/Lateral x-ray imaging				X	[X]	X	[X]	X	[X]	[X]	[X]	[X]
Paresthesia Questionnaire								X	X	X	X	X
Patient Global Impression of Change								X	X	X	X	X
Subject Satisfaction								X	X	X	X	X
Adverse Event Monitoring	X		X	X	X	X	X	X	X	X	X	X
Device Programming				X		X	[X]	[X]	[X]	[X]	[X]	[X]
Device Log								[X]	[X]	[X]	[X]	[X]
Cross over									[X]			
Study Completion					X ^a							X

^a For subjects that do not have a successful Trial Phase.

[X] Optional activity.

B.9.2. Statistical Analysis

Descriptive statistics will be used to summarize baseline and outcome data collected during the study. Continuous variables will be summarized using means, standard deviations, and ranges. Categorical variables will be summarized in frequency distributions. Repeated measures models will account for within subject correlation by use of a compound-symmetric covariance structure (based on logistic regression/generalized estimating equations for binary variables, and linear repeated measures models for continuous variables).

B.9.2.1 Primary Analyses

The *primary efficacy endpoint* will be evaluated with a Farrington-Manning binomial test for non-inferiority with a 10% margin at the one-sided 0.05 alpha level.

H_0 : The percentage of subjects (P) who achieve a 50% improvement in their back VAS pain score at 3 months in the Test group is inferior to that in the Control group.

$$P_{\text{Test}} \leq P_{\text{Control}} - 10\%$$

H_1 : The percentage of subjects (P) who achieve a 50% improvement in their back VAS pain score at 3 months in the Test group is not inferior to that in the Control group.

$$P_{\text{Test}} > P_{\text{Control}} - 10\%$$

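### The only listed analysis of change from before crossover to month 12 (B.7.5) is unworkable as written: it censors the month-12 values it needs

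*Combined protocol and SAP*

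**What the plan says.** Section B.7.5 (Additional Data Collection) includes the item "Comparison of mean change from last visit prior to crossover to 12 months visit. This analysis censors data post-crossover". It does not name the outcome variable, the population or the groups compared, and it is not taken up again in B.9.2.3.

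B.6.14 sets who may cross: "subjects in both arms will have an option to change to the other arm if the subject is not receiving sufficient pain relief". B.6.1 says the same of implanted subjects, "but are not getting sufficient pain relief and would like to try the other treatment arm's parameters". On timing, B.6.1 states "Crossover must be completed within 30 days of the 6 month visit" and B.6.14 states "The subject can crossover immediately after completing the 6 month assessment or within 30 days after completing the 6 month assessment". Table 1 allows ±31 days around the 6-month visit and ±45 days around the 12-month visit.

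Three other provisions bear on the item:

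- The closing bullet of B.7.5 has the additional items analysed by the treatment a subject is on at each time point, not by randomized arm.
- B.9.2.4 leaves analyses outside the primary endpoint unimputed unless stated otherwise.
- B.7.1, B.7.4 and B.9.2.2 specify repeated measures models by current treatment. B.7.1 adds sensitivity analyses that censor after crossover, and B.7.4 does so for the responder comparison.

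**The concern.** The item defines a change that starts before crossover and ends at month 12, then removes everything observed after crossover. For a crosser the end point of the change is one of the values removed. For a subject who stays on the assigned programming, the starting visit is undefined.

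The two-way crossover is a design feature named in the synopsis, and this is the only listed analysis of what happened within the subjects who used it. As it stands, the programmer must either report nothing or choose a repair after data are in hand, in an open-label study. The most obvious repair, deleting the censoring sentence and doing nothing else, brings in a second problem. Subjects cross because relief is poor at about the visit that becomes the reference, and no comparator is named.

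**Working it through.** The plan states no figure for this item, so there is nothing to reproduce. The check has four steps.

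**1. Timing.** Inputs are the Table 1 windows and the 30-day limit in B.6.1 and B.6.14, with a month taken as 365.25/12 = 30.44 days.

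- Latest on-schedule crossover: 6 × 30.44 + 31 + 30 = 243.6, about day 244.
- Earliest in-window month-12 visit: 12 × 30.44 - 45 = 320.25, about day 320.
- Gap: 320.25 - 243.6 = about 76 days.

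Even at the extremes of both windows, a crosser's month-12 value comes after crossover.

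**2. Who contributes data.**

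| Group | Pre-crossover visit | Month-12 value | Usable change |
|---|---|---|---|
| Crossed on schedule | Yes (month 6) | Censored, not imputed | None |
| Never crossed | Not defined | Observed | None |

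The closing bullet of B.7.5 would keep the post-crossover values under current treatment. The two instructions cannot both be applied.

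**3. If only the censoring sentence is removed.** Suppose switching has no effect, the VAS mean and SD are stable, and subjects with month-6 VAS above a threshold cross. Under a normal approximation the expected change from month 6 to month 12 is

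-(1 - ρ) × SD × λ, with λ = φ(k)/(1 - Φ(k)) and k = (threshold - mean)/SD.

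The documents give none of these inputs. Assumed ranges: month-6 mean 3.0 or 4.0 cm, SD 2.0 or 2.5 cm, threshold 3.5 or 5.0 cm, and correlation ρ between months 6 and 12 of 0.5 to 0.9.

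| Case | Mean | SD | Threshold | ρ | Apparent change (cm) |
|---|---|---|---|---|---|
| Smallest | 4.0 | 2.0 | 3.5 | 0.9 | -0.13 |
| Middle example | 4.0 | 2.5 | 5.0 | 0.7 | -0.80 |
| Largest | 3.0 | 2.5 | 5.0 | 0.5 | -1.71 |

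For the middle example, k = (5.0 - 4.0)/2.5 = 0.4 and λ = 1.07, so the change is -(0.3)(2.5)(1.07) = -0.80 cm. The yardstick is the 0.65 cm secondary non-inferiority margin in B.9.2.2. That is a between-arm margin, used here only for scale.

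**4. Would a month-3 reference remove the problem?** With selection on month 6, the expected change from month 3 to month 12 is (ρ between months 6 and 12, minus ρ between months 3 and 6) × SD × λ. Under the compound-symmetric structure of B.9.2 the two correlations are equal and the result is 0. If correlation decays, it is not. Assume mean 3.2, SD 2.5, threshold 4.0 and a correlation of 0.8 per 3 months. Then k = 0.32, λ = 1.01, and the change is (0.64 - 0.80)(2.5)(1.01) = -0.40 cm. With 0.9 or 0.7 per 3 months it is -0.23 or -0.53 cm. If correlation is constant but subjects judge relief on the average of months 3 and 6, it is -0.75 to -0.26 cm for correlations of 0.5 to 0.8. Month 3 therefore reduces the artefact but need not remove it.

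**The case against.** The strongest reply is that the item can be read another way. Crossover is tied to the 6-month visit, so the starting point could mean that visit for everyone. The item would then compare the arms on change from month 6 to month 12 among subjects who stayed, with crossers censored. That would have data and would match the censored analyses elsewhere. But it needs a pre-crossover visit for subjects who never cross, and the text does not supply one. It may be what the authors meant; it is not what the item says.

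Second, a reader might infer from this item that the trial has no usable analysis of crossover. The documents do not support that. B.7.1, B.7.4 and B.9.2.2 specify models by current treatment, with censored versions in B.7.1 and B.7.4, and all of these have data. They are also open to selection by outcome. What they do not give is the change within crossers from before to after the switch.

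Third, the regression-to-the-mean argument concerns a repaired analysis, not one in the plan, and its size rests on assumed inputs. This stands. The plan sets no VAS threshold for crossing and nowhere says a change in crossers would be credited to the therapy they moved to. The argument is a reason to repair the item with care, not a finding of existing bias.

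Fourth, the item is additional data with no hypothesis or alpha, and B.8.2 sets no success criterion beyond the primary. This also stands and limits the importance of the point.

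**Conclusion.** The point holds as a defect in a stated rule. No subject who crosses on schedule has a usable end point, and no subject who stays has a defined starting point. This rests only on the plan's own dates, its censoring sentence and its no-imputation rule. The conflict with the closing bullet of B.7.5 is also textual.

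The second part is conditional. If the item is repaired only by dropping the censoring, and switching does nothing, crossers could still appear to improve by about 0.1 to 1.7 cm. The direction follows from selection on poor relief near the reference visit, given a stable mean and imperfect correlation. The size depends on the assumed mean, SD, threshold and correlation, and it is small when correlation is high. It would be too strong to say that a spurious benefit will be reported; the documents support only that one could be mistaken for benefit.

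The primary endpoint and the 3-month secondary tests precede crossover and are unaffected. The item should be corrected, but it does not threaten the main conclusion.

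**What to change.** In B.7.5, and in the separate statistical analysis plan that B.9.2.4 mentions:

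- Delete the second sentence of this item, which censors post-crossover data, and say how the item relates to the closing bullet on current treatment.
- Define the analysis as the change in back-pain VAS from the 6-month visit, as the last visit before crossover, to month 12 in subjects who crossed. Report it separately for Conventional to DTM and DTM to Conventional.
- Beside each, show the same change in 6-month non-responders from the same randomized arm who did not cross. These subjects chose to stay, so they are a reference and not a control.
- Show the change from the 3-month visit as a sensitivity display, stating that it reduces but does not necessarily remove regression to the mean.
- Label the result descriptive and not attributable to crossover alone.

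The cost is wording and slightly more analysis work, since VAS is already collected at months 3, 6, 9 and 12. An apparent crossover benefit may look smaller once the comparison group is beside it.
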